7.2 Adherence to the Clinical Investigation Plan

A deviation is defined as an event where the clinical investigator, site personnel, sponsor or sponsor representative did not conduct the clinical study according to the Clinical Investigational Plan, IRB/EC requirements or the Investigator Agreement. The investigator is not allowed to deviate from the CIP, except as specified under emergency circumstances.

In some cases, failure to comply with the CIP may be considered failure to protect the rights, safety and well-being of subjects, since the non-compliance exposes subjects to unreasonable risks. For example, failure to adhere to the inclusion/exclusion criteria: these criteria are specifically defined by the Sponsor to exclude subjects for whom the device is not beneficial and the use involves unreasonable risks. This may be considered failure to protect the rights, safety and well-being of the enrolled subject. Similarly, failure to perform safety assessments intended to detect adverse events may be considered failure to protect the rights, safety and well-being of the enrolled subject. Investigators should seek minimization of such risks by adhering to the CIP.

Simultaneously, in the event that adhering to the CIP might expose the subject to unreasonable risks, the investigator is also required to protect the rights, safety and well-being of the subject by intentionally deviating from the requirements of the CIP, so that subjects are not exposed to unreasonable risks.

It is the responsibility of the investigator to provide adequate medical care to a subject enrolled in a study.

Regulations require that the PI maintain accurate, complete, and current records, including documents showing the date of and reason for every deviation from the Clinical Investigational Plan. Relevant information for each deviation will be documented on a Deviation Case Report Form. The site will submit the CRF to SJM.

Regulations require Investigators obtain approval from SJM and the IRB/EC [as required] before initiating changes in or deviations from the protocol, except when necessary to protect the life or physical well-being of a subject in an emergency.

Prior approval must be requested when the PI anticipates, contemplates, or makes a conscious decision to depart from the CIP, except when unforeseen circumstances are beyond the investigator's control (e.g. a subject who fails to attend a scheduled follow-up visit, a subject is too ill to perform a CIP-required test, etc.). All deviations, including those beyond the investigator's control, must be reported on a Deviation CRF.

To obtain approval, the Principal Investigator may call or email and discuss the potential deviation with SJM or designee prior to initiating any changes.

The investigator is required to adhere to local regulatory requirements for reporting deviations to IRB/EC. All deviations must be reported to appropriate regulatory authorities in specified timelines (if appropriate).

Investigator will notify SJM and the reviewing IRB/EC within 5 working days of:

- Any deviation to protect the life or physical well-being of a subject in an emergency
- Any failure to obtain informed consent

Investigators or the designee must notify SJM, Inc. as soon as possible and complete the Deviation CRF.

7.3 Repeated and serious non-compliance

In the event of repeated non-compliance or a one-time serious non-compliance, as determined by the Sponsor, a Clinical Research Associate or clinical representative will attempt to secure compliance by one or more of the following actions:

- Visiting the investigator
- Contacting the investigator by telephone or in writing
- Retraining of the investigator

If an investigator is found to be repeatedly non-compliant with the signed agreement, the CIP or any other conditions of the clinical study, the Sponsor will either secure compliance or, at its sole discretion, terminate the investigator's participation in the clinical study.

8.0 ADVERSE EVENT, ADVERSE DEVICE EFFECT, DEVICE DEFICIENCY

8.1 Definitions

8.1.1 Adverse Event (General Definition)

An adverse event in general is any untoward medical occurrence, unintended disease or injury, or untoward clinical signs (including abnormal laboratory findings) in subjects, users or other persons, whether or not related to the medical device under study.

This definition includes events unrelated to the study medical device, the comparator or procedures involved: adverse event (AE) and serious adverse event (SAE).

It also includes events, which are related to the study medical device, the comparator or the procedures involved: adverse device effect (ADE) and serious adverse device effect (SADE).

Only Serious Adverse Events (SAE), Adverse Device Effects (ADE) and Serious Adverse Device Effects (SADE) will be collected in this study.

8.1.2 Serious Adverse Event (SAE)

Any untoward medical occurrence, which was not related to the study device, procedure or comparator, but resulted in serious injury to a subject or other person. A serious adverse event is one that led to:

- Death

- A serious deterioration in the health of the subject, that either resulted in:
 - A life-threatening illness or injury OR
 - A permanent impairment to a body structure or a body function OR
 - An in-patient or prolonged hospitalization OR
 - A medical or surgical intervention to prevent life-threatening illness or injury or permanent impairment to a body structure or a body function
- Fetal distress, fetal death or a congenital abnormality or birth defect

A planned hospitalization for a pre-existing condition, or a procedure required by the CIP is not considered a serious adverse event.

8.1.3 Adverse Device Effect (ADE)

An adverse event related to the use of a study medical device when the occurrence does not meet the definition of serious.

This definition includes adverse events resulting from insufficient or inadequate instructions for use, deployment, implantation, installation, or operation, or any malfunction of the study medical device.

This definition includes any event resulting from the use error or from intentional misuse of the investigational study medical device.

8.1.4 Serious Adverse Device Effect (SADE)

An adverse event that happens in a subject or other person, is related to the study device, comparator, or procedure, and has resulted in any of the consequences characteristic of a serious adverse event.

8.2 Procedure for assessing, recording and reporting device deficiencies/complaints, adverse device effects, serious adverse events and serious adverse device effects:

The safety surveillance and the safety reporting, both performed by the investigator, will start as soon as the subject is enrolled in this study (date of signature of the informed consent and an attempted implant/ablation procedure) and will continue until the last study visit has been completed, the subject is deceased, or the subject/investigator withdraws the subject from the study, except as otherwise specified in the CIP.

All reportable adverse event data (as described below) including deaths and device deficiency data (if applicable) will be collected throughout the clinical study and will be reported to the Sponsor on a dedicated case report form or through the EDC system. The Investigator will record all reportable adverse events and device deficiencies (if applicable) on the appropriate case report forms.

Reportable adverse events will be monitored until they are adequately resolved. Records related to the subject's subsequent medical course must be maintained and submitted (as applicable) to the Sponsor. The status of the subject's condition will be documented at each visit.

Reportable events to sponsor are considered:

- All Adverse Device Effects (ADEs) (including procedure related events)
- All Serious Adverse Device Effects (SADEs) (including procedure related events)
- All Serious Adverse Events (SAEs)
- All Device Deficiencies (DD) (if applicable), that could have led to a serious adverse device effect
 - if either suitable action had not been taken;
 - if intervention had not been made or
 - if circumstances had been less fortunate

All ADEs, SADEs, SAEs and DD are to be documented and reported to the sponsor within 10 calendar days for US sites and 3 calendar days for sites outside US after becoming aware of the event or per local regulatory timelines.

The Sponsor will ensure that all events and device deficiencies are reported to the relevant authorities as per regulations.

Additional information may be requested, when required, by the Sponsor in order to support the reporting of AEs to regulatory authorities.

For unexpected failure modes or unexpected adverse events, the US site should follow their standard reporting practices for medical device reporting (MDR). As defined in 21 CFR 803, a MDR reportable event (or reportable event) means: An event that device user facilities become aware of that reasonably suggests that a device has or may have caused or contributed to a death or serious injury. A device user facility must report deaths and serious injuries that a device has or may have caused or contributed to, establish and maintain adverse event files, and submit summary annual reports to FDA.

8.3 Subject Death

8.3.1 Procedure for recording and reporting subject death

All patient deaths that occur during this investigation must be reported to St. Jude Medical within 10 days of the center becoming aware of the death for US sites and within 3 calendar days of the center becoming aware of the death for non-US sites. Investigator will complete the Patient Death form. Patient's death is an Early Conclusion of the subject's participation in the study. Therefore, beside completion of a Death CRF, the investigator is required to complete the Termination/Withdrawal form and Product Out of Service CRF.

Patient death may be an outcome of an adverse event. If the death is related to an AE, all the efforts to get AE details should be made by the investigator and an Adverse Event CRF should be completed in addition to the Patient Death CRF. If there are no AEs associated with death, completion of Patient Death CRF will be sufficient.

By completing the electronic Death CRF the sponsor will be automatically notified. In case of EDC failure, notify Sponsor via [contact] or via Fax (please refer to the Investigator Site Binder, "Sponsor Contact Details" for further details about Fax numbers).

It is the investigator's responsibility to notify the IRB/EC, if appropriate, in accordance with national and local laws and regulations.

Every attempt should be made to explant the pulse generator and/or leads intact. Any explanted devices or leads should be returned to St. Jude Medical for analysis promptly. The reason the pulse generator and/or lead(s) are not being returned to St. Jude Medical must be stated clearly on the Death or Out of Service form.

8.4 Device Deficiency (DD)

A Device Deficiency is defined as an inadequacy of a medical device with respect to its identity, quality, durability, reliability, safety or performance.

DD include malfunctions, use errors and inadequate labeling.

SJM will appropriately document and manage all DDs.

Device deficiencies in SJM market-released products must be reported per SJM product surveillance process. Please notify SJM Tech Service via email at [contact]

9.0 DATA MANAGEMENT

Overall, the Sponsor will be responsible for the data handling.

The sponsor and/or its affiliates will be responsible for compiling and submitting all required reports to governmental agencies.

SJM respects and protects personally identifiable information that we collect or maintain. As part of our commitment, SJM is certified to the U.S. - European Union Framework and U.S. – Swiss Safe Harbor Framework Agreements regarding human resources and subject clinical trial personal information. The privacy of each subject and confidentiality of his/her information will be preserved in reports and when publishing any data. Confidentiality of data will be observed by all parties involved at all times throughout the clinical study. All data will be secured against unauthorized access.

Data will be submitted through appropriate forms in EDC. Additional source documents will be submitted via EDC, email, fax, etc.

The Principal Investigator or institution will provide direct access to source data during and after the clinical study for monitoring, audits, IRB/EC review and regulatory authority inspections. As required, the Principal Investigator or institution will obtain permission for direct access to source documents from the subject, hospital administration and national regulatory authorities before starting the clinical study.

9.1 Data Management Plan

A detailed Data Management Plan will be established to ensure consistency of the data. This document will include procedures used for data review, database cleaning, and issuing and resolving data queries. If appropriate, the DMP may be updated throughout the study duration. All revisions will be tracked and document controlled.

CRF data will be captured in a validated electronic database management Oracle Clinical system hosted by SJM. Only authorized site personnel will be permitted to enter the data through the electronic data capture (EDC) system deployed by SJM. An electronic audit trail will be used to track any subsequent changes of the entered data.

9.2 Document and data control

9.2.1 Traceability of documents and data

The investigator will ensure accuracy, completeness, legibility and timeliness of the data reported to the sponsor on the CRFs and in all required reports.

9.2.2 Recording data

Source documents will be created and maintained by the investigational site team throughout the clinical study.

The data reported on the CRFs will be derived from, and be consistent with, these source documents, and any discrepancies will be explained in writing.

The following data can be recorded directly in the CRFs

- Fluoroscopy time
- Radiation exposure
- Time for steps in the study
- MediGuide™-enabled tools used
- Fluoroscopic views and orientation angles used

The CRFs will be signed and validated by the authorized site personnel.

10.0 MONITORING

Centralized monitoring will occur through routine internal data review. This monitoring is designed to identify missing and inconsistent data, data outliers, and potential protocol deviations that may be indicative of site non-compliance. On site monitoring may occur at the discretion of the sponsor.

11.0 REGULATORY INSPECTIONS

The investigator and/or delegate should contact SJM immediately upon notification of a governmental agency inspection at the site. A clinical monitor or designee will assist the investigator and/or delegate in preparing for the audit.

An investigator who has authority to grant access will permit authorized governmental agency employees, at reasonable times and in reasonable manner, to enter and inspect any establishment where devices are held (including any establishment where devices are used or where records or results are kept).

An investigator, or any person acting on behalf of such a person with respect to the study, will permit authorized governmental agency employees, at reasonable times and in reasonable manner, to inspect and copy all records relating to the study.

An investigator will permit authorized governmental agency employees to inspect and copy records that identify subjects, upon notice that governmental agency has reason to suspect that adequate informed consent was not obtained, or that reports required to be submitted by the investigator, to the Sponsor or IRB/EC have not been submitted or are incomplete, inaccurate, false or misleading.

12.0 STATISTICAL CONSIDERATIONS

12.1 Statistical design, hypotheses, method and analytical procedures

In this study, no randomization or cross-over will be used. Analysis of the study objectives will be done using descriptive summary statistics such as the mean, standard deviation, n, and range or a percentage along with the numerator and denominator of that percentage. Ninety-five percent confidence intervals constructed around the estimated means or percentages will also be calculated.

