Previous single-center studies have shown that the application of the MediGuide™ technology can lead to a significant reduction in fluoroscopy burden during ablations of atrial flutter, SVT, and atrial fibrillation.⁸⁻¹² In a recent single-center registry,¹³ the MediGuide™ navigation system was used for over 600 cases of ablations for atrial flutter, atrial fibrillation and ventricular tachycardia and implantation of cardiac resynchronization therapy (CRT) devices. In these cases, the median fluoroscopy time was not only reduced compared to the traditional fluoroscopy time but the complication rate was lower than previously-published data. It was also observed by the same group that the total fluoroscopy time and the exposure to radiation was reduced further as the operator gained more experience in working with MediGuide™ system and tools.¹⁴ However, these studies were all conducted at a single center and the radiation reduction benefit, complication rate, and operator proficiency across clinics at different geographies are unknown.

The MediGuide registry is sponsored by SJM. The goal of this study is to collect data on the clinical utility of MediGuide™ system in CRT implantation and study-specific EP procedures.

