4.0 STUDY DESIGN

4.1 Purpose

The intent of this worldwide registry/observational study is to understand the utility of the MediGuide™ technology in real world clinical practice during CRT implantation and study-specific-EP procedures. The study should provide an understanding of the effect of MediGuide™ technology on:

- The amount of fluoroscopy time and the radiation exposure
- Total procedure time
- Peri-procedural clinical event rate

Additionally, this study will address the following

- Identification of procedural challenges which future MediGuide tools can potentially address
- Evaluation of newly available tools during the study

- Correlation between MediGuide™ operator experience and the radiation exposure amount and time

This study may continue for up to 3 years, depending on the rate of enrollment and follow-up timelines.

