12.2 Sample size

This is a worldwide, multicenter, non-randomized registry/observational study that aims to enroll up to 1000 patients from up to 65 centers undergoing either CRT implantation or an EP procedure. The study will enroll a minimum of 250 patients for each group. This sample size was chosen to provide understanding on the effect of following MediGuide™ technology on.

- The amount of fluoroscopy time and the radiation exposure
- Total procedure time
- Peri-procedural clinical event rate

12.3 In multi-center studies, the minimum and maximum number of subjects to be included for each center

The maximum number of subjects that each center can enroll is 50 patients.

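### Does the peri-procedural clinical event rate need a pre-specified numerator before this descriptive registry can report it?

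*Combined protocol and SAP*

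**What the plan says.** Section 4.1 lists "Peri-procedural clinical event rate" as one of three things the registry should inform, and the Synopsis repeats it. Section 12.2 names the same three when it justifies the numbers enrolled: "This sample size was chosen to provide understanding on the effect". The term is not defined anywhere.

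Section 12.1 is descriptive. For percentages it asks for "a percentage along with the numerator and denominator of that percentage", with a 95% confidence interval.

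The events available come from section 8.1.1: "Only Serious Adverse Events (SAE), Adverse Device Effects (ADE) and Serious Adverse Device Effects (SADE) will be collected in this study". The classes do not overlap for a single event:

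- SAE (8.1.2) is serious and unrelated: "which was not related to the study device, procedure or comparator, but resulted in serious injury".
- SADE (8.1.4) is serious and related to the device or procedure.
- ADE (8.1.3) is non-serious and related: "An adverse event related to the use of a study medical device when the occurrence does not meet the definition of serious". Section 8.2 extends its reporting to procedure-related events.

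Section 2.0 supplies the motive. In an earlier single-center registry, "the complication rate was lower than previously-published data", while across centers "the radiation reduction benefit, complication rate, and operator proficiency across clinics at different geographies are unknown".

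**The concern.** Three classes allow at least four numerators: SADE alone, all serious (SADE and SAE), all related (SADE and ADE), or all three. Section 4.1 speaks of clinical events without limiting them to related ones. Section 2.0 speaks of complications, which suggests related ones. The reporting list in 8.2 does not settle the matter, because it also contains device deficiencies that harmed nobody.

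In a registry the estimate is the product. If the numerator is not fixed in advance, it could be chosen with the data in view. A favourable choice might then be set beside published complication rates, and the confidence interval would not reveal it.

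**Working it through.** **What the text settles.**

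- Denominator: section 4.4.2 defines enrolled patients as those with consent and an attempted procedure.
- Window: surveillance starts at enrollment (8.2) and participation ends at the pre-discharge visit (6.6).
- Unit: a percentage with numerator, denominator and confidence interval is ordinarily a proportion of patients.
- Events: 8.1.1 closes the set. Table 1 in section 6.2 has a single row for reportable adverse events, and 6.4.1 asks for nothing else at pre-discharge.
- Device deficiencies: 8.4 defines them as inadequacies of a device, so they are not clinical events in a patient.
- Timing: no section says when the numerator will be chosen. The text supports only that it is not pre-specified.

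What stays open is whether unrelated SAEs belong in the headline rate.

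**How much that matters.** Section 12.2 gives no expected rate or precision target, so there is no figure of the plan's own to reproduce. The class shares below are assumptions, with each patient counted once.

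Let p be the share of patients with any collected event, and u the share whose only collected event is an unrelated SAE. Then

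- rate on all classes = p
- rate on related events = p − u
- gap = u
- 95% half-width = 1.96 × √(p(1 − p)/n)

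For example, at p = 8% and n = 250: 1.96 × √(0.08 × 0.92/250) = 3.4 points.

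The group sizes are the minimum of 250, an even split of 1000 (500), and the largest single group possible (1000 − 250 = 750).

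| SADE / ADE only / SAE only | All classes | Related | Gap | Half-width, n = 250 | n = 500 | n = 750 |
|---|---|---|---|---|---|---|
| 2 / 2 / 1% | 5% | 4% | 1 | 2.7 | 1.9 | 1.6 |
| 3 / 4 / 1% | 8% | 7% | 1 | 3.4 | 2.4 | 1.9 |
| 4 / 6 / 2% | 12% | 10% | 2 | 4.0 | 2.8 | 2.3 |
| 2 / 3 / 2% | 7% | 5% | 2 | 3.2 | 2.2 | 1.8 |

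Gaps and half-widths are in percentage points. The gap is inside the half-width in every row at 250 and 500. At 750 it is outside in the last row only (2.0 against 1.8). With all 1000 patients pooled, the last row gives 2.0 against 1.6.

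At n = 250 the gap would exceed the half-width only if unrelated SAEs were the sole event in more than 2.7/5 = 54%, 3.4/8 = 42% or 4.0/12 = 34% of affected patients, at p = 5%, 8% and 12%. Over a window from the procedure to discharge, shares that high seem unlikely, though the documents give no data on it.

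**The narrower numerators.** For the first three rows, SADE alone gives 2%, 3% and 4%, which is 3, 5 and 8 points below the all-class rate and outside the half-width each time. Serious events only (SADE and SAE) gives 3%, 4% and 6%, which is 2, 4 and 6 points below, and outside the half-width in the second and third rows. Neither has support in the text. The objective is not limited to serious events, and the registry collects ADEs expressly.

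**The ADE wording.** Section 8.1.3 names only the device, while 8.2 makes procedure-related ADEs reportable. Read together they capture those events, so this is a clerical mismatch.

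**The case for a change.** The strongest reply is that writing the definition down costs one sentence and needs no new data, whereas leaving it out relies on good faith. Showing the numerator tells a reader what was counted but does not fix it beforehand. A difference in definition also does not shrink as patients accrue, while sampling error does. The large-sample results above bear this out, so a gap within the half-width at 250 is not a general guarantee. And section 2.0 invites comparison with published complication rates, which depends on the definition used.

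All of this stands as a reason why a written definition would be tidier. It does not show that the plan produces a wrong result. The comparison with published rates is background and is not a planned analysis. No test, error rate or decision depends on the figure. Because the classes are recorded separately and do not overlap for a single event, every version of the rate can be tabulated at reporting with nothing lost. A reader who wants the related rate can be given it alongside the all-class rate.

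**Conclusion.** The omission is real but minor, and no change follows. It is a gap that analysts would fill sensibly: patients with at least one SAE, SADE or ADE up to pre-discharge, over all enrolled patients in each group, with related and serious subsets beside it. Restricting the count to related events would lower the rate by 1 to 2 points in the assumed examples, against half-widths of 2.7 to 4.0 points at 250 per group.

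This rests on the assumed class shares, on the all-class and related readings being the only two with textual support, and on the analysis staying purely descriptive. If the rate were to be tested against an external benchmark, the numerator would have to be fixed first.
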